# 3.2.2 Secondary Study Endpoints

NA

Identification of baseline factors (e.g., age, MNSI [56], general activity) predictive of improvement, represented as the baseline to follow-up change in each outcome.

# 4 Study Enrollment and Withdrawal

# 4.1 Inclusion Criteria

In order to be eligible to participate in this study, an individual must meet all of the following criteria:

- 1. Be 40-70 years old
- 2. Have a clinical diagnosis of Type 2 diabetes
- 3. Have clinical symptoms of DPN potentially including lack of monofilament and vibration perception
- 4. Have a BMI less than 40 kg/m^2 (due to magnet bore restrictions)
- 5. Be vaccinated for COVID-19

# 4.2 Exclusion Criteria

An individual who meets any of the following criteria will be excluded from participation in this study:

- 1. Serious cardiac pathology or musculoskeletal problems that would limit exercise ability
- 2. MNSI score < 1
- 3. Current open wound or history of plantar ulcer for the last 3 months
- 4. Stroke or other central nervous system pathology
- 5. Stage 2 hypertension (resting blood pressure >160 systolic or >100 diastolic)
- 6. Contraindications to 3T whole body MRI scanners (e.g., pacemaker, cerebral aneurysm clip, cochlear implant, presence of shrapnel in strategic locations, metal in the eye, claustrophobia, or other problems).
- 7. Subjects with alcoholism, chronic drug use, chronic gastrointestinal disease, or renal or hepatic impairment
- 8. Pregnant women and children

# 4.3 Vulnerable Subjects

Diabetes affects approximately 26 million people in the US and although prevalence may differ among different races and ethnicities, no population is spared. Age and sex-adjusted rates for diabetes by race have been reported as: Asian Americans 8.4%, non-Hispanic whites 7.1%, Hispanic/Latinos 12.6%, non-Hispanic blacks 15.3%, American Indians/Alaska natives 14.2%. From those diagnosed, 49% are women and 51% are men. Our targeted/planned subject enrollment will reflect the diverse racial and ethnic patient population that is served by the NYU Hospitals' system. This system functions as one of the main referral centers for lower Manhattan, Queens, and Brooklyn.

DPN is one of the most common complications of T2DM. Nerve damage in DPN is likely due to combination of factors including high blood glucose, long duration of diabetes, and abnormal fat levels. It is generally accepted that among children with T2DM, DPN is very rare. Therefore, children will be excluded from this study.

If a volunteer is an employee, student, or resident of NYU Langone Health or its affiliates, their decision to participate, decline participation, or withdraw from the study will have no impact on the individual's employment, academic standing, or grades. Record of the participation cannot be linked to an academic record.

The justification for enrolling this population is due to the strict inclusion/exclusion criteria we have for this study. We are not directly targeting the recruitment of NYU students/employees, however, if we come across an eligible candidate who is an NYU student/employee, we want to be able to enroll him/her into our

### CONFIDENTIAL

This material is the property of the NYU School of Medicine and Langone Medical Center. Do not disclose or use except as authorized in writing by the study sponsor Behavioral Intervention Template Version: 5 MAY 2017

study. Recruitment is conducted by the PIs, research coordinator(s), and other study team members. Anyone who recruits or consents for this study has no role in grading or evaluating students.

The consent process is conducted in a private room where the study procedures and risks are explained to the subject. A photocopy of the signed consent form is given to the subject. The consent process is appropriate for the research being conducted. Often times an eligible patient's treating physician is called to ask if the physician objects to study participation for the patient. This extra screening step is done for the purpose of maximizing protection against risks and minimizing any coercion.

This study consists of multiple visits which allow the study team the opportunity to frequently discuss with the subject that his/her participation is voluntary. In order to ensure this is done, the study's case report forms include a task to remind the participant that withdrawal from the study is possible at any time. In order to minimize breaches of confidentiality, all participants are assigned a subject ID number upon study enrollment. The ID number is not associated with the subject's name or any other identifying information. Only the subject's ID and initials are used when collecting and recording data. The case report forms and source documentation are kept in a binder that is stored in a locked cabinet, in a locked room. Only Radiology Department staff have the code to the room with the binders.

# 4.4 Strategies for Recruitment and Retention

Participants who meet our study's criteria will be recruited from collaborating clinics at NYULH, DataCore at NYU, through direct advertising via social media (Craigslist) or brochures/flyers, and from existing relationships with prior research subjects. Interested individuals will complete a structured telephone screening and/or online eligibility screening survey. Eligible individuals will be invited to participate in the study.

Our recruitment methods/materials may include a link to an online eligibility screening survey. The content of the survey will be submitted to the IRB for approval. PHI will be collected as a result of completing the screening form. If the subject is not eligible to participate, PHI will be destroyed immediately.

### 4.4.1 Use of DataCore/Epic Information for Recruitment Purposes

This study will utilize DataCore and EPIC for recruitment purposes. DataCore will be used to generate a report of potential participants that meet this study's eligibility criteria. Additionally, study team member(s) will perform weekly EPIC screenings of patients at collaborating NYULH clinics until target enrollment is achieved.

The following data points and PHI will be used:

- First and last name
- Contact information
- Clinical diagnoses and medications
- Office visit notes
- Medical Record Number (MRN)
- Treating Physician (TP)

The IRB-approved study personnel who will have access to the EPIC search results are the following:

- Principal Investigator
- Co-Investigator
- Study Coordinator
- Research Coordinator
- Research Data Associate

Once potential subjects have been identified, they will be contacted in one of the following ways:

#### CONFIDENTIAL

This material is the property of the NYU School of Medicine and Langone Medical Center. Do not disclose or use except as authorized in writing by the study sponsor Behavioral Intervention Template Version: 5 MAY 2017

- The TP will be notified by email or in person that they have an eligible patient. He/she may tell the patient about this research opportunity and may provide recruitment materials. He/she may also obtain the patient's permission to be contacted by study staff (in person or by telephone).
- The study team may access contact information from medical records through DataCore to contact patients directly.
- They may receive an approved recruitment message to their MyChart account. Recipients can respond to indicate whether they are interested in participating.

If a subject requests information regarding opting out of further recruitment for all research, subjects will be directed to contact [contact] or [name].

# 4.4.2 Use of Craigslist for Recruitment Purposes

Craigslist will be used for recruitment. The ad will be posted under "community > volunteers." The language in the ad will be submitted to the IRB for approval.

# 4.4.3 Direct Advertising

Our team will use brochures, flyers, and other IRB-approved recruitment materials to provide information to interested individuals. We plan to distribute recruitment materials in spaces that we expect our target population to frequent. We will seek approval from the establishment or facilities management prior to posting. Locations that we expect to distribute to include, but are not limited to, collaborating NYULH clinics and physicians, private non-NYULH clinics (i.e. local podiatry clinics), residential buildings, senior centers, libraries, community centers, etc.

# 4.5 Duration of Study Participation

Participants will be enrolled for a minimum of 10 weeks. We anticipate that some participants will be enrolled for greater than 10 weeks due to challenges associated with scheduling study procedures (limited availability on the MRI scanners). Additionally, we are allowing a one-week grace period during the intervention for patients who express pain/soreness due to the exercise regimen, or for other circumstances (i.e., planned vacation).

# 4.6 Total Number of Participants and Sites

Recruitment will end when approximately 40 participants are enrolled across one site.

# 4.7 Participant Withdrawal or Termination

## 4.7.1 Reasons for Withdrawal or Termination

Participants are free to withdraw from participation in the study at any time upon request. An investigator may terminate participation in the study if:

- Any clinical adverse event (AE), laboratory abnormality, or other medical condition or situation
  occurs such that continued participation in the study would not be in the best interest of the
  participant
- The participant meets an exclusion criterion (either newly developed or not previously recognized) that precludes further study participation

## 4.7.2 Handling of Participant Withdrawals or Termination

If a participant misses an intervention session, they will be contacted by study personnel and reasons for missing the session will be documented. We will seek written permission to contact participants and will reach them using their preferred method (phone or email). If attendance drops below 80%, reimbursement will be pro-rated based on the number of sessions completed. Participants will be allowed

a grace period/extension of one week. If participants miss more than one consecutive week, participation will be considered terminated.

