#### CONFIDENTIAL

This material is the property of the NYU School of Medicine and Langone Medical Center. Do not disclose or use except as authorized in writing by the study sponsor Behavioral Intervention Template Version: 5 MAY 2017 If a participant chooses to withdraw from the exercise intervention, they will be contacted by study personnel and reasons for withdrawal will be documented. We will seek written permission to contact participants and will reach them using their preferred method (phone or email). Reasons for withdrawal will be classified as related or unrelated to intervention. Participants will be invited to complete endpoint testing even if they choose to withdraw from the intervention.

Participants that cannot complete the study due to incompatible logistics (precipitating from i.e. covidrelated study suspension or personal leave of absence) will be encouraged to continue the study at a later date. Participants with long-term absences will be re-consented and will re-perform all study procedures in the longitudinal protocol described in section 6. Such participants will be considered newly enrolled and must meet all inclusion/exclusion criteria laid out in section 4. Long-term absence is defined as: 1) greater than 3-months between Step 2: Blood draw (section 6.4.1.2) and Post-non-exercise phase visit (section 6.4.3) or 2) greater than 4-months between Post-non-exercise phase visit (section 6.4.6).

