## 6.4.4 Post-Exercise Phase Visit

Participants will undergo blood tests, VO2R, and a final MRI to compare with results collected prior to the exercise intervention. The final visit should occur within two weeks after the last exercise session. This will allow for feasible scheduling, data collection, and study completion considerations.

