# 9.3.2 Analysis of the Primary Efficacy Endpoint(s)

A matched-pairs Wilcoxon signed rank test will be applied to the within-subject change in each outcome among subjects demonstrating full compliance with the exercise program. Additionally, weighted analysis of covariance (ANCOVA) will be used to test the change in each outcome adjusting for the measured level of compliance using data from all subjects. The values of each outcome at

CONFIDENTIAL

baseline and follow-up for all subjects will be the dependent variable and the ANCOVA model will include time (baseline versus follow-up) as the within-subject factor of interest covariates, the measure of compliance as numeric covariate and an anonymized subject ID as a classification factor so that the comparison of times will be based on their within-subject difference. The secondary objective is to assess the extent to which exercise induced improvements in DTI outcomes are can be at least partially explained by reduction in ROS will be addressed using linear regression, The baseline to follow-up change in each outcome will be the dependent variable and the model will include the measure of compliance as a numeric factor and the within-subject change in ROS as the numeric factor of interest. A second regression will be conducted with baseline factors (e.g., age, MNSI, general activity) added to the model in order to identify factors predictive of improvement in each outcome.

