### 9.3.4 Adherence and Retention Analyses

The analysis will follow the intention-to-treat (ITT) principle and include data from every subject irrespective of whether the subject was compliant with the assigned intervention. A quantitative assessment of compliance with the intervention, ranging from 0 (complete non-compliance) to 1 (full compliance), will be included as a weighting factor to allow more compliant subjects to contribute more to the analysis. The weight for the control phase will be set to 1 since subjects are not required to exercise.

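### Endpoint testing is offered in words only to participants who choose to withdraw, so someone stopped under the one-week rule has no stated route to the post-exercise assessment

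*Combined protocol and SAP*

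**What the plan says.** All references are to the combined protocol and SAP.

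- **One-week rule (4.7.2).** After allowing a one-week extension, the section states: "If participants miss more than one consecutive week, participation will be considered terminated". It does not say whether this means participation in the exercise programme or in the study.
- **Investigator termination (4.7.1).** "An investigator may terminate participation in the study if" an adverse event, another medical reason or an exclusion criterion makes it appropriate.
- **Endpoint testing (4.7.2, repeated in 6.4.5 Withdrawal Visit).** "Participants will be invited to complete endpoint testing even if they choose to withdraw from the intervention". Neither place mentions participants who were terminated.
- **Logistics provision (4.7.2).** "Participants that cannot complete the study due to incompatible logistics", for example because of a COVID-related suspension or a leave of absence, are encouraged to resume later. After a long absence they re-consent and restart as new enrolments.
- **Assessments (Attachment A).** After exercise, MRI, MNSI, OGTT and bloodwork are each scheduled once, at Week 18.
- **Analysis (9.3.2, 9.3.4).** One primary test is run "among subjects demonstrating full compliance with the exercise program". A weighted ANCOVA is run "adjusting for the measured level of compliance using data from all subjects". The stated principle is ITT, to "include data from every subject irrespective of whether the subject was compliant with the assigned intervention", with compliance from 0 to 1 as a weight. The Protocol Summary and 1.2 repeat the principle.
- **Sample size (4.6, 9.4).** About 40 are enrolled and 40 are counted as analysed. The plan does not say how missing follow-up values are handled.

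**The concern.** Section 4.7.2 covers both withdrawal and termination, but the route to endpoint testing is written for withdrawal alone. A participant who stops and says so is invited back. One who misses more than a week and is terminated by rule is not, on the literal wording. Section 4.5 gives exercise-related pain or soreness as a reason for using the grace period, so a participant whose pain lasts longer could meet the rule.

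The ANCOVA in 9.3.2 includes subject ID, so the time comparison rests on within-subject differences. A participant with no Week 18 value adds nothing to that comparison. If those lost improved less than those who finished, the all-subjects analysis would drift towards an analysis of adherers while still being described as ITT. An outcome that was not collected cannot be recovered at the analysis stage.

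**Working it through.** **1. Who has a stated route to the post-exercise assessment?**

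| How the participant stops | Text that applies | Endpoint testing stated? |
|---|---|---|
| Chooses to withdraw from exercise | 4.7.2, 6.4.5 | Yes |
| Absent for logistic reasons | 4.7.2 | Yes, by resuming or restarting |
| Misses more than one consecutive week, other reason | 4.7.2 | Not stated |
| Terminated by the investigator | 4.7.1 | Not stated |

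**2. The plan's own power figure.** Inputs from 9.4, Tables 3 and 4 (exercise): BOLD baseline 3.24, change 1.11 (SD 1.26); PCr baseline 41.16, change 10.61 (SD 12.85); MNSI baseline 5.2, change 1.20 (SD 1.78). Method: paired t-test, two-sided 5%, 80% power, noncentral t distribution. At n = 40 the detectable standardised change is 0.4543.

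- BOLD: 0.4543 × 1.26 / 3.24 = 17.7% of baseline
- MNSI: 0.4543 × 1.78 / 5.2 = 15.5%
- PCr: 0.4543 × 12.85 / 41.16 = 14.2%

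The stated upper limit of 18% is reproduced. The stated lower limit of 10% would fit the control-phase PCr SD of 8.53 if its baseline were about 38.7, but that baseline is not legible. The anticipated changes also reproduce: 1.20/5.2 = 23.1%, 10.61/41.16 = 25.8%, 1.11/3.24 = 34.3%.

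**3. Power if some final visits are lost.** Section 1.2 says only that attrition was low in preliminary studies, so losses of 4 and 8 are assumptions.

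| Analysed | Detectable BOLD change | Power, BOLD 1.11 | Power, PCr 10.61 | Power, MNSI 1.20 |
|---|---|---|---|---|
| 40 | 17.7% | >99.9% | 99.9% | 98.6% |
| 36 | 18.7% | 99.9% | 99.8% | 97.6% |
| 32 | 19.9% | 99.8% | 99.5% | 95.8% |

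**4. Effect on the weighted mean change.** Let k of 40 be stopped, with compliance weight c and a change equal to f times that of completers (who have weight 1). The ratio of the weighted mean with them to the mean without them is

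R = [(40 − k) + k·c·f] / [(40 − k) + k·c],

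and leaving them out overstates the change by 1/R − 1. Half of the 30 sessions (3 a week for 10 weeks) gives c = 15/30 = 0.5.

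| k | c | f | R | Overstatement |
|---|---|---|---|---|
| 4 | 0.5 | 0 | 36/38 | 5.6% |
| 4 | 0.2 | 0 | 36/36.8 | 2.2% |
| 4 | 0.8 | 0 | 36/39.2 | 8.9% |
| 4 | 0.5 | 0.5 | 37/38 | 2.7% |
| 8 | 0.5 | 0 | 32/36 | 12.5% |

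In the first row, if completers have the Table 4 BOLD change of 1.11, the weighted mean is 1.11 × 36/38 = 1.05 with the stopped participants and 1.11 without them.

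**The case against.** **The wording can be read more kindly.** The one-week rule sits in a paragraph about missed exercise sessions. Section 4.7.1 adds the words in the study when it means the study, and the rule does not, so it may end only the exercise programme. The invitation to endpoint testing is phrased with even if, which can be heard as a general invitation extended to withdrawers. Both readings are fair. A reader might infer that the plan definitely ends follow-up for these participants; the documents do not settle that. What stands is that no sentence invites them, and staff could reasonably follow either reading.

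**Investigator terminations are largely safety stops.** They include newly found exclusion criteria, among them MRI contraindications and pregnancy. Not recalling such people for a fasting OGTT and MRI is often right. This stands, and it is why the main point is the one-week rule.

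**A timing fault might also be inferred.** Section 6.4.4 says: "The final visit should occur within two weeks after the last exercise session". One could conclude that an early stopper would be measured weeks ahead of schedule. But 6.4.4 governs the Post-Exercise Phase Visit; people who leave the intervention come under 6.4.5, which sets no date. Whether to test near stopping or at the planned date is a design preference, so this inference is not supported.

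**ITT wording.** Including everyone irrespective of compliance is not a promise of complete data, and an invitation does not guarantee attendance. This stands. The gap works against the stated aim without flatly contradicting it.

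**The effect is small.** The full-compliance Wilcoxon test excludes these participants anyway, and low weights shrink their influence elsewhere. In the central scenario BOLD moves by 0.06, about 0.3 of its standard error (1.26/√40 = 0.20). This also stands. An unweighted calculation would give a larger figure (40/36 − 1 = 11.1% for four lost with no change), but it ignores the planned compliance weighting.

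**Conclusion.** The point holds as a gap in wording with a modest consequence. Taken literally, a participant stopped under the one-week rule, outside the logistics provision, has no stated route to the only post-exercise outcome assessment. Outcomes can therefore go missing in relation to adherence in the analysis meant to use all subjects.

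Under the assumed losses, the overstatement of the mean change is about 5.6% in the central case and 2.2% to 12.5% across the scenarios. These figures depend on the assumed number lost, the compliance reached and the change in those lost; the documents give none of these. If the stopped participants changed as much as completers (f = 1), there would be no overstatement.

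A reader might infer that the trial's power is at risk. It is not: at the anticipated changes, power stays above 95% with 32 analysed. The detectable BOLD change does pass the stated 18% at n = 36 (18.7%), but that is well short of the 34% anticipated for BOLD. The change is worth making because it is cheap and because uncollected outcomes cannot be recovered.

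**What to change.** 1. In 4.7.2, state that missing more than one consecutive week ends the exercise programme but not study follow-up, with the logistics provision in the same section as the exception.
2. In 4.7.2 and 6.4.5, extend the endpoint-testing invitation to participants stopped under the one-week rule, and to those terminated by the investigator where testing is safe and not contraindicated.
3. Analyse them with the compliance weight they achieved, as 9.3.4 already provides.

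**Cost.** One short amendment, and staff effort to bring stopped participants back for a visit already planned. No additional participants are needed. Some will decline, so missing outcomes will be reduced but not eliminated.

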#### CONFIDENTIAL

This material is the property of the NYU School of Medicine and Langone Medical Center. Do not disclose or use except as authorized in writing by the study sponsor Behavioral Intervention Template Version: 5 MAY 2017 If a participant chooses to withdraw from the exercise intervention, they will be contacted by study personnel and reasons for withdrawal will be documented. We will seek written permission to contact participants and will reach them using their preferred method (phone or email). Reasons for withdrawal will be classified as related or unrelated to intervention. Participants will be invited to complete endpoint testing even if they choose to withdraw from the intervention.

Participants that cannot complete the study due to incompatible logistics (precipitating from i.e. covidrelated study suspension or personal leave of absence) will be encouraged to continue the study at a later date. Participants with long-term absences will be re-consented and will re-perform all study procedures in the longitudinal protocol described in section 6. Such participants will be considered newly enrolled and must meet all inclusion/exclusion criteria laid out in section 4. Long-term absence is defined as: 1) greater than 3-months between Step 2: Blood draw (section 6.4.1.2) and Post-non-exercise phase visit (section 6.4.3) or 2) greater than 4-months between Post-non-exercise phase visit (section 6.4.6).

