# 3 Study Design and Endpoints

# 3.1 Description of Study Design

This single-center, longitudinal design study uses multinuclear-MRI to evaluate the mechanistic effects of exercise on skeletal muscle function and peripheral nerve integrity in patients with DPN, and to determine whether exercise can reverse DPN symptoms. Forty DPN patients will be enrolled and be prescribed a 10-week exercise program following a 4-week non-exercise period. The exercise program will comprise aerobic and resistance components; a moderate level of intensity will be calculated based on results from a maximal graded exercise test (VO2R) conducted prior to the intervention. Multinuclear-MRI data will be acquired at baseline, as well as before and after the intervention that can provide mechanistic insight into the adaptations in lower leg muscle function and peripheral nerve integrity of patients with DPN, and their role in improving DPN symptoms.

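### A participant who restarts after a long absence counts as newly enrolled, so one person can hold two subject IDs and fill two of the 40 places; the plan needs a one-person rule and a complete definition of the trigger

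*Combined protocol and SAP*

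**What the plan says.** The restart rule is in section 4.7.2. It applies to "Participants that cannot complete the study due to incompatible logistics", for example because of a COVID-related suspension or a leave of absence. "Participants with long-term absences will be re-consented and will re-perform all study procedures in the longitudinal protocol described in section 6". Then: "Such participants will be considered newly enrolled and must meet all inclusion/exclusion criteria laid out in section 4".

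A long absence has two limbs. The first is "greater than 3-months between Step 2: Blood draw (section 6.4.1.2) and Post-non-exercise phase visit (section 6.4.3". The second is "greater than 4-months between Post-non-exercise phase visit (section 6.4.6", after which the sentence ends without naming a second visit.

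Other sections give the rule its effect:

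- 6.4.1.1 treats a person as enrolled once the consent form is signed, and a restarter signs again.
- 4.3 assigns the subject ID at enrolment.
- 4.6 ends recruitment at about 40 enrolled participants.
- 9.3.2 puts an anonymised subject ID into the ANCOVA as a classification factor.
- 9.3.4 says the ITT analysis will "include data from every subject irrespective of whether the subject was compliant with the assigned intervention" and gives the control phase a weight of 1.
- 9.4 bases power on 40 subjects in the analysis.

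On the order of phases, 3.1 says patients will "be prescribed a 10-week exercise program following a 4-week non-exercise period". No section says whether a restarter keeps the old ID, whether the two records are linked, or which attempt supplies the analysed changes. Earlier exposure to the study exercise is not among the exclusions in 4.2.

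**The concern.** The analysis treats each subject ID as a separate, independent person. The restart rule can give one person two IDs. Two consequences follow.

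First, the number of people studied can fall below 40 while the number enrolled reads 40. A person who restarts under the second limb has already reached the post-non-exercise visit and so already has a control-phase change. The repeat produces another. Both would enter the exercise-versus-control comparison in 9.3 as if they came from different people.

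Second, the interval in the second limb begins just before the exercise phase, so such a restarter may have trained for some weeks before the new baseline. Retained benefit could shrink the new exercise change, and detraining could shift the repeat control-phase change.

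The trigger itself is also incomplete: with one visit named, the second limb does not define an interval.

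**Working it through.** **1. The plan's own figure.** 9.4 states 80% power at two-sided 5% with 40 subjects for a change of 10% to 18% of the baseline mean. Inputs are the exercise baseline means (Table 3: BOLD 3.24, PCr 41.16, MNSI 5.2) and the SDs of change (Table 4: 1.26, 12.85, 1.78). The normal formula is (1.96 + 0.84) × SD / √n / baseline mean. For BOLD: 2.80 × 1.26 / 6.325 / 3.24 = 17.2%. PCr gives 13.8% and MNSI 15.2%. The exact paired t calculation gives 17.7%, 14.2% and 15.5%. The upper end of 18% is reproduced. The lower end cannot be confirmed, because the control-phase baselines are not legible in the copy reviewed.

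**2. What a first attempt contributes.**

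| Restart under | Control-phase change in first attempt | Exercise change in first attempt | Study exercise before new baseline |
|---|---|---|---|
| First limb | Normally none | None | None |
| Second limb | Yes | Usually none | Possible |

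The duplicated quantity is therefore mainly the control-phase change, and only for second-limb restarters.

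**3. Size of the duplication.** Let k of 40 records be repeats and let r be the correlation between a person's two control-phase changes. The documents give neither, so both are assumptions. The true variance of the mean change is the naive variance × (1 + 2kr/40). For k = 4 and r = 0.5: 1 + 4/40 = 1.10, and 1 − 1/√1.10 = 4.7%. For r = 0.25 to 0.75, taking every restart as second-limb:

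| k | Variance factor | Control-phase SE too small by | True alpha of a nominal 5% test of that change (t, 39 df) |
|---|---|---|---|
| 2 | 1.025–1.075 | 1.2%–3.6% | 0.053–0.058 |
| 4 | 1.05–1.15 | 2.4%–6.7% | 0.056–0.067 |
| 8 | 1.10–1.30 | 4.7%–12.3% | 0.061–0.084 |

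These figures are for the control-phase change, not for the exercise change.

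**4. Fewer people for the exercise change.** If the k first attempts have no exercise change, 40 − k people remain:

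| k | People | Detectable change: BOLD / PCr / MNSI | Power for the anticipated MNSI change (the lowest of the three) |
|---|---|---|---|
| 0 | 40 | 17.7% / 14.2% / 15.5% | 98.6% |
| 2 | 38 | 18.1% / 14.6% / 16.0% | about 98% |
| 4 | 36 | 18.7% / 15.0% / 16.4% | 97.6% |
| 8 | 32 | 19.9% / 16.0% / 17.5% | about 96% |

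BOLD moves slightly beyond the stated 18%. The anticipated changes are 1.11/3.24 = 34.3%, 10.61/41.16 = 25.8% and 1.20/5.2 = 23.1%, so power for them stays high.

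**5. Prior exercise.** Attachment A puts the MRI scans at weeks 1, 5 and 18 and the exercise at weeks 7 to 16. The pre-exercise and final scans are 18 − 5 = 13 weeks apart. If the second limb runs to the post-exercise visit (an assumption), four months is about 4 × 52/12 = 17.3 weeks, which leaves about 4 weeks of slack. A person could pass the limit after doing much of the programme. If a fraction f of the exercise effect is still present at the new baseline, the mean exercise change is multiplied by 1 − f × k/(40 − k). With k = 4 and f = 0.5 this is 1 − 0.5 × 4/36 = 0.94; with k = 8 and f = 0.5 it is 1 − 0.5 × 8/32 = 0.875. Here too f is assumed and all k are taken as second-limb.

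**6. Section references.** The second limb cites 6.4.6. In the contents list 6.4.6 is the post-exercise visit and 6.4.3 the post-non-exercise visit. In the body the post-exercise visit is 6.4.4 and no 6.4.6 exists.

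**The case against.** The strongest reply is that the documents never say a returner takes a second ID or a second place. The Protocol Summary, 3.1 and 9.3.1 all speak of 40 patients, and a careful team would count people. This is fair as to intent. But 4.7.2 states a rule rather than leaving a silence, and 4.3, 4.6 and 6.4.1.1 attach the ID, the count and the status to enrolment. Nothing overrides them for restarters.

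Several stronger readings are tempting and do not stand:

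- *A reader might infer that the first non-completion vanishes and attrition is understated.* The text does not say so. 4.7.2 provides that "If participants miss more than one consecutive week, participation will be considered terminated", and section 8 has attrition reviewed quarterly. In the analysis set, double counting and a lost dropout are alternatives: if the first record is kept, the non-completion is visible; if it is dropped, the person counts once.
- *A reader might apply the standard-error figures to the exercise comparison.* That needs two exercise changes per person, which someone who could not complete the first attempt usually lacks. A partial attempt with an endpoint would be down-weighted by compliance.
- *A reader might conclude that restarters' changes are biased toward zero.* First-limb restarters have had no study exercise. Second-limb restarters repeat the 4-week non-exercise phase, so their new pre-exercise scan has some washout. The new enrolment scan, which 9.3.1 uses as the starting point, comes before that phase and is less protected. Retained benefit would shrink the exercise change, while detraining during the repeat control phase could widen the contrast with it. The direction is not determined.
- *A reader might take it that the study was suspended for COVID.* Section 4.7.2 gives this only as an example of a cause.
- *A reader might say the second limb cannot be applied at all.* The contents list makes the intended visit guessable. It is still a guess.

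**Conclusion.** The point holds in a limited form. As written, the rule allows one person to have two IDs, two of the 40 places and two supposedly independent entries in the model. The main statistical effect is a duplicated control-phase change for people who restart under the second limb, with possible carry-over or detraining in their repeat data.

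The effect is probably small. With 2 to 4 restarts, the control-phase standard error is 1% to 7% too small and power for the anticipated exercise changes is barely touched. With 8 restarts the true alpha for the control-phase change could reach about 0.08. All of this rests on assumed numbers of restarts, correlations and retained effects. The incomplete second limb and its mismatched section numbers are plain drafting defects that need no assumption.

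**What to change.** In 4.7.2, 4.6, 9.3.2 and 9.3.4, state that:

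1. Each person keeps one permanent ID across attempts, and that ID is the subject factor in the model.
2. Each person counts once toward 40.
3. Each person contributes one control-phase change and one exercise-phase change to the primary analysis. The rule for choosing the attempt is fixed in advance. A sensitivity analysis uses the alternative attempt and also excludes restarters with prior study exercise. Which attempt is primary is a trade-off for the sponsor: the first is usually incomplete, and the second may follow exposure.
4. First attempts are reported as non-completions in the participant flow, and study exercise already done is recorded.
5. The second limb names its second visit, and the section references match the body. The rule that ends participation after a missed period and the encouragement to continue later, both in 4.7.2, must also be reconciled.

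The cost is a few sentences and no new procedures. Re-entrants no longer top up the enrolment count, so reaching 40 people may take a few more recruits.
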